1.2.5 Confirmed or suspected COVID-19

Confirmed or suspected cases of COVID-19 will not be considered to impact the definition of the intervention effect of interest, and the post-ICE data will be included in the analyses ('Treatment policy' strategy). This is assuming that the participant remains in the study.

This strategy only applies to confirmed or suspected COVID-19. Other ICEs or protocol deviations related to COVID-19 (treatment or study discontinuation) should be handled using the approaches outlined in the sections above.

Study participants are permitted to receive the COVID-19 vaccine at any point in the study. A treatment policy strategy will be used for this ICE where post-vaccination data is kept as part of the analyses.

1.2.6 Study termination and loss to follow-up

A participant may withdraw from the study at any time at his/her own request or may be withdrawn at any time at the discretion of the Investigator for safety, behavioral, IMP compliance, or administrative reasons. If a study participant withdraws or is withdrawn, he or she should be encouraged to perform the End-of-Treatment (EOT) Visit and the Safety Follow up Visit approximately 30 days after last dose of IMP.

Study termination will only be considered treatment-related if the reason for termination is 'lack of efficacy'. As a default approach, MAR will be assumed and the implicit imputation of likelihood-based linear models (for gaussian distributed outcomes), will be applied to any occurrence of study termination (including treatment-related termination) and the event will be ignored. For event-based outcomes, the approach will depend on whether the termination is considered to be treatment-related or not. For treatment-related termination, imputation assuming non-response to treatment will be applied (for example, for time to ST initiation we would impute treatment-related termination as a progression-related 'event'). For other causes of study termination (including loss to follow-up) data will be considered right censored at the time of termination (and ignored).

In well-designed clinical studies it is reasonable to assume that dropout patterns follow the MAR mechanism, although missing not at random (MNAR) data cannot be ruled out (Liu-Seifert, 2015). As an alternative approach, a different hypothetical strategy, such as a reference-based imputation (RBI) approach (for gaussian distributed outcomes) will be used when participants terminate the study for treatment-related reasons for MDS-UPDRS-based continuous endpoints estimands (Appendix 5).

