#### Estimator

Monotone missing data from participants who dropped out of the study will be imputed using reference-based imputation (RBI) and according to ST intake status.

Imputed datasets for those dropouts will be summarized into a single dataset to obtain Month 12 estimates, which will then be combined with the de-mediated Month 12 estimates.

An analysis of covariance (ANCOVA) will be applied to the complete Month 12 data. Treatment will be included in the model as a categorical fixed effect, gender, age at Baseline, and Baseline MDS-UPDRS Part III subscale (ePD subscore) data will be fitted as covariates.

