1.2.2 Treatment discontinuation and treatment-related ICE-like protocol deviations

Participant-led or Investigator-led treatment discontinuation may be related to assigned investigational treatment (due to lack of efficacy / AEs) or unrelated.

Note that some of the participants who discontinue assigned investigational treatment due to lack of efficacy (whether on placebo or UCB0599) may want to start taking ST and therefore their data will be handled as such.

Treatment discontinuation will not be considered to impact the definition of the intervention effect of interest, and the post-ICE data will be included in the analyses ('Treatment policy' strategy).

Minor treatment-related protocol deviations such as IMP treatment non-compliance (missing a dose or taking a dose at a different time of the day) or minor drug administration error will not be considered to impact the definition of the intervention effect of interest and the post-ICE data will be included in the analyses ('Treatment policy' strategy).

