To increase information regarding DaT-SPECT SBR signal, participants intending to terminate the study (assumed to be 10% by 12 months) should have a scan before study termination (as part of the EOT visit). Participants who choose to withdraw from the study at or after 6 months and accept to have a scan at time of study termination will have their scan analysed as if it was taken at 12 months.

Residual data attrition due to study termination and loss to follow-up may be imbalanced between treatment arms by the time participants reach the 18-month timepoint, creating selection bias. This imbalance could happen in different directions depending on the balance of efficacy to AEs in the study. Compared to the placebo arm:

- a larger number of participants could be lost in the UCB0599 arms compared to placebo due to treatment-related AEs;
- a smaller number of participants could be lost in the UCB0599 arms compared to placebo due to treatment-related efficacy.

Consequently, different numbers and subtypes of participants per arm may continue to the end of the study. We estimate we would be left with an imbalance between arms of 5% due to data loss to follow-up, and another 5% data loss due to study termination before 6 months, as well as another 5% in the period between 12 and 18 months.

For these participants, we will control for bias at the analysis stage using implicit imputation of likelihood-based approaches (see [Section 5.3](#)).

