In addition, implementation of the g-estimation requires that the missing data be imputed *a priori*. Intermittent missing data will be imputed assuming missing at random (MAR). Longitudinal/monotone missing data from participants who discontinued the study for reasons unrelated to randomized treatment or who are lost to follow-up (due to unknown reasons by definition) will be imputed assuming MAR, while longitudinal/monotone missing data from participants who discontinued the study for reasons related to randomized treatment (i.e. due to lack of efficacy) will be imputed assuming missing not at random (MNAR), using a relatively simple Reference-Based Imputation approach (RBI), i.e. control-based pattern imputation. As the 3 endpoints of interest are continuous, we will adopt multiple imputation (MI) approaches.

The application of reference-based imputation (RBI) for some of the MNAR data also represents a case of uncongeniality to the analysis model: the imputation model is uncongenial with the analysis model (Bartlett & Hughes, 2020). Therefore, to obtain adequate estimates of standard errors for the point estimates of interest, the recommended approach is to first bootstrap the trial data, then impute via MI. In our case, we will adopt the so-called MI Boot Percentile approach as implemented by (section 3.2.1 in Bartlett & Hughes, 2020), where first $B = 200$ bootstrap samples of the data are generated, then $M = 10$ imputations of each B bootstrap sample are generated to obtain $B \times M$ datasets for each endpoint. G-estimation models are then applied to each of the $B \times M$ dataset, followed by the analysis model(s) and the relevant parameters mean and corresponding (robust) 95% bootstrap percentile-CI are then obtained through the approach outlined below. Note that to be conservative, RBI data from participants who discontinued the study for reasons related to randomized treatment will not be ST de-mediated.

Schematic of the Methodological Approach

1. Bootstrap observed data B times, by randomized treatment group (described in [Section 6.5.3](#))
2. For each B bootstrap sample, use MI to impute missing data M times, according to MAR or MNAR paradigms (described in [Section 6.5.4](#))
3. Apply g-estimation once to each $B \times M$ dataset (described in [section 6.5.5](#)), excluding participants who discontinued the study for reasons related to randomized treatment

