6.5.3 Bootstrapping

- Prior to bootstrapping and in preparation for imputation of longitudinal/monotone missing data (see [section 6.5.4](#)), participants will be classified as having monotonic missing data either for reason not related to randomized treatment, or for reasons related to randomized treatment. Participants who discontinued randomized treatment for lack of efficacy prior to study termination or loss-to-follow-up will be included in the latter case.
- Sampling with replacement of each endpoint dataset
- Balanced sampling: sample for each randomized treatment arm separately (STRATA statement)
- Bootstrap **B = 200** times (using **B** as specified in the so-called MI Boot Percentile approach implemented by Bartlett & Hughes, 2020 section 3.2.1)
- Bootstrap using SAS PROC SURVEYSELECT procedure with options METHOD=URS, OUTHITS and SAMPRATE=1.

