 - And for ALL participants, the intermittent missing values will be filled in using the MI-MCMC method, with a total of **M=10** sets of imputations being performed, using data from the same randomized treatment arm subset;
 - For participants randomized to active treatment with monotone MAR data or participants randomized to Placebo, missing data will be imputed by applying monotone regression on these 10 intermittent missing-imputed subsets, using data from the same randomized treatment arm subset;
For participants randomized to active treatment with monotone MNAR data, missing data will be imputed by applying monotone regression on these 10 intermittent missing-imputed subsets, using data from the randomized placebo arm subset. If any issues are encountered using the monotone MI assuming MNAR approach, a monotone MI assuming MAR approach will be used instead.

Imputed dataset from participants with monotone MAR and MNAR data will be stacked back together to reconstitute the full list of trial participants for each imputed set.

- For each **B** bootstrap sample, the **M**-imputed randomized treatment arm subsets will be stacked again into **M** complete imputed datasets corresponding to a single bootstrap sample (full trial).
- If values outside of the pre-defined range of values for MDS-UPDRS endpoints (defined as the minimum and maximum values which could be observed) are imputed, they will be reset to the relevant lower or upper limit of the range after completion of the MI procedure
 - MDS-UPDRS Part I-III sum score: 0 – 236
 - MDS-UPDRS Part III subscale: 0 – 132
 - MDS-UPDRS Part III subscore: 0 – 60
 - MDS-UPDRS Part II subscale: 0 – 52
 - MDS-UPDRS Part I subscale: 0 – 52

At the end of the imputation process, **B x M** complete datasets will be available.

For all imputation models, sex (reference = Male), age at informed consent signing (agegrp4, reference = 60-69), and geographic region (reference = Europe) will be included as baseline demographics. No missing data is expected for baseline demographics. MI models will only allow continuous variables. Therefore, categorical variables will be re-coded as indicator variables as follows:

Baseline demographics (included in all analyses)

- For sex: Male = 0, Female = 1
- For age at informed consent: 60-69 = 0, 40-49 = 1, 50-59 = 2, 70+ = 3
- For geographic region: Europe = 0, North America = 1

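### In the Appendix 5 de-mediated MDS-UPDRS analyses, active-arm participants who leave because of drug-related adverse events are imputed from their own arm, which in expectation credits them with continued benefit

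*SAP*

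**What the plan says.** SAP 1.2.6 sets the definition: "Study termination will only be considered treatment-related if the reason for termination is" lack of efficacy. Appendix 5 carries it into the imputation for the symptomatic-treatment (ST) de-mediated estimands. In SAP 6.5.1, monotone missing data from participants who left "for reasons related to randomized treatment (i.e. due to lack of efficacy) will be imputed assuming missing not at random (MNAR"), by a control-based model. SAP 6.5.3 widens that class in one direction only: "Participants who discontinued randomized treatment for lack of efficacy prior to study termination or loss-to-follow-up will be included in the latter case". Adverse events have no counterpart. For every other active-arm dropout, SAP 6.5.4 states that "missing data will be imputed by applying monotone regression on these 10 intermittent missing-imputed subsets, using data from the same randomized treatment arm subset".

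Four other passages bear on this:

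- Protocol 9.3.1.1.3 (Month 12, Part III and ePD): "Monotone missing data from participants who dropped out of the study will be imputed using reference-based imputation (RBI"). Protocol 9.3.1.2.3.1 gives the same rule for Month 18. Neither limits it by reason for leaving.
- SAP 3.4 expects that "a larger number of participants could be lost in the UCB0599 arms compared to placebo due to treatment-related AEs", as one of two possible directions of imbalance.
- SAP 1.2.2 says that stopping study drug "may be related to assigned investigational treatment (due to lack of efficacy / AEs) or unrelated". It handles all such stopping by treatment policy, as does SAP Table 1-2.
- SAP 6.2, which lists changes from the protocol-planned analyses, does not mention that reference-based imputation was narrowed to lack-of-efficacy exits.

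**The concern.** Treatment policy for drug discontinuation means that the scores of interest after stopping are the scores off drug. A participant who stops because of an adverse event and then leaves has missing values that are mostly off-drug values. MAR imputation from the same active arm draws on participants who are mostly still on drug. Little off-drug data will be there to correct this, because participants who stop study medication early are asked to attend the End of Treatment and Safety Follow-up visits (Protocol 6.8; SAP 5.1.2.1.3), not the remaining schedule. If the drug works, the imputed values carry benefit that these participants would not be expected to keep.

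Protocol 2.3 names hypersensitivity as an identified risk and hepatotoxicity as a potential one, so exits of this kind are foreseeable. SAP section 2 asks that interpretation weigh effect sizes and confidence intervals, so a favourable shift in an estimate matters even in an exploratory study. No planned analysis tests it: the only sensitivity analysis for the primary estimand adds prognostic covariates (SAP 5.3.1.3), and SAP 6.5.4 lets even the lack-of-efficacy group revert to MAR if problems arise.

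**Working it through.** **1. The plan's own figure.** Inputs from SAP 3.1 and Table 3-1: random-intercept variance 154.0, random-slope variance 0.43, residual variance 31.1, placebo slope 0.90 points/month, N1·Var(T) = 85.57, Z = 2.56, equal allocation. Then:

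- σ² = 154.0 + 31.1 = 185.1
- 1 − ρ = 31.1/185.1 = 0.1680
- r·N1Var(T) = 0.43 × 85.57/185.1 = 0.1988
- Δ² = 0.27²/185.1 = 0.0003938
- n = 2 × (0.1680 + 0.1988) × 2.56²/(85.57 × 0.0003938) = 142.66

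This rounds up to the stated 143 per arm, so these inputs are a fair basis for the effect size. The sample size does not depend on the imputation rule.

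**2. Design effect at Month 12.** 0.27 points/month × 12 = 3.24 points on the Part I-III sum score.

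**3. Benefit retained at Month 12 by an active-arm participant last seen at Month 6.**

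- MAR from own arm: 3.24 in expectation.
- Jump-to-reference: 0.
- Copy-reference: the placebo regression of Month 12 on Months 0, 2, 4 and 6, with covariance 154.0 + 0.43·s·t (plus 31.1 when s = t), applied to the accrued benefit 0.27·t. This gives 1.34. It is the closest of the three to the placebo-model regression in SAP 6.5.4.
- Copy-increments: 0.27 × 6 = 1.62.

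**4. Expected arm difference** when a fraction d of the active arm leaves this way: 3.24(1 − d) + d × (retained benefit). Overstatement is 3.24 divided by that, minus 1.

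| d (assumed) | Jump | Copy-reference | Copy-increments | Overstatement by MAR (same order) |
|---|---|---|---|---|
| 2% | 3.18 | 3.20 | 3.21 | 2.0%, 1.2%, 1.0% |
| 5% | 3.08 | 3.15 | 3.16 | 5.3%, 3.0%, 2.6% |
| 10% | 2.92 | 3.05 | 3.08 | 11.1%, 6.2%, 5.3% |

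The top row of the range, 10%, is the termination rate from all causes by 12 months assumed in SAP 3.2. The adverse-event share is not given.

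**5. Scale.** At d = 10% the gap is 0.162 to 0.324 points. The design standard error of the Month 12 difference is 3.24/2.563 = 1.264, so the gap is 0.13 to 0.26 of it. That standard error belongs to the primary slope model and serves here only as a yardstick.

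**6. Part III and ePD.** Two of the rules are free of scale if benefit accrues linearly. At d = 10%, jump-to-reference gives 1/0.90 = 1.111, and copy-increments gives 1/(1 − 0.10 × 6/12) = 1/0.95 = 1.053. The 5% to 11% range therefore carries over at Month 12. At Month 18 with the same d, copy-increments gives 1/(1 − 0.10 × 12/18) = 1.071, so about 7% to 11%.

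The arithmetic assumes untreated placebo progression after exit. SAP 6.5.4 imputes before de-mediation and ignores ST status, so actual placebo-based draws would carry some ST effect.

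**The case against.** The best defence is that MAR fits the stated target. Protocol 4.2 and SAP 1.1 aim at efficacy rather than effectiveness, and Protocol Table 9-2 handles study termination by a hypothetical strategy. That is a reasonable reading for termination in itself. But supposing that the participant had not left does not put them back on drug: discontinuation remains under treatment policy, so the values to be filled in are still off-drug values.

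It can also be said that nothing was hidden. The lack-of-efficacy definition is logged under SAP Amendment 2, Amendment 4 records that de-mediation may use other imputation strategies, and Protocol 9.5 refers to the SAP for imputation details. This stands as far as it goes. The de-mediated sum-score estimand is a SAP addition with no protocol imputation rule to depart from. For Part III and ePD the protocol does state a rule, and SAP 6.2 is where a change to it should appear.

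Several stronger readings are tempting, and the documents do not support them:

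- *The primary analysis is biased by this definition.* SAP 1.2.6 applies MAR likelihood methods to every termination there, treatment-related or not, so the label has no effect. The same holds for the other mixed models outside Appendix 5. In the event-based analyses, adverse-event exits are right-censored, not imputed.
- *SAP 1.2.2 flatly contradicts 1.2.6.* The former concerns stopping drug, the latter leaving the study, and 1.2.2 says only that stopping may be treatment-related. SAP 3.4 is the better evidence of tension.
- *Adverse-event exits will cluster on active and lack-of-efficacy exits on placebo.* SAP 3.4 says only that imbalance could occur, in either direction.
- *Adverse-event losses of 15% are to be expected.* That exceeds the planned 10% for all causes.

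**Conclusion.** The point holds for the Appendix 5 de-mediated estimands and no further. Control-based imputation omits the exits that SAP 3.4 itself singles out as a possible source of extra active-arm loss, and for Part III and ePD this narrows a protocol rule without being listed in SAP 6.2.

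The size is modest: about 5% to 11% of the Month 12 difference if all of the planned 10% terminations on active were adverse-event exits last seen at Month 6, and about 1% to 2% if 2% were. This rests on three assumptions: the drug has its design effect, benefit accrues linearly, and leavers lose some or all of it after stopping. MAR also conditions on each participant's own history and on any off-drug visits in the arm, so the credit is an expectation, not a certainty for each person. With no drug effect the rules agree in expectation; a reader might infer type I error inflation, but none follows.

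The status of these estimands adds to the case for settling this. SAP Table 1-2 marks the Part III and ePD means as key secondary, while SAP 1.2.1 and 6.2 call the de-mediated estimands supplementary.

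**What to change.** In Appendix 5, add a separate flag, set before unblinding, for terminations due to adverse events judged drug-related, including drug discontinuation for such an event before termination. Leave the SAP 1.2.6 definition alone: it also drives the time-to-event coding, which need not change. Limit the flag to drug-related events, because Protocol 9.5.2 treats exits known to be unrelated to study drug as uninformative and SAP 1.2.4 does the same for death and serious injury.

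Pre-specify, at least as a sensitivity analysis of the de-mediated estimands, control-based imputation of the flagged participants' monotone missing data. Do not simply move them into the existing lack-of-efficacy class. That class is left out of the g-estimation (SAP 6.5.1, 6.5.5), so anyone who had started ST would keep uncorrected scores. Keep their observed data in the g-estimation, and state how ST is handled in their imputed values.

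For Part III and ePD, either restore the protocol's reference-based imputation for dropouts or list the departure and its rationale in SAP 6.2.

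The cost is one flag, some wording, one more run of the bootstrap and imputation pipeline, and possibly a slightly less favourable estimate.

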1.3 Study design

PD0053 is a randomized, double-blind, placebo-controlled, 18-month Phase 2a study to evaluate the efficacy, safety, tolerability, and PK of orally administered UCB0599 in study participants with early PD who are not treated with symptomatic medications targeting motor symptoms of PD at the time of inclusion. Oral UCB0599 capsules or matching placebo capsules will be administered BID, approximately 12 hours apart.

The primary objective of the study is to demonstrate the superiority of UCB0599 over placebo with regard to clinical symptoms of disease progression over 12 and 18 months in this patient population. The difference between UCB0599 and placebo will be evaluated for both the low and high doses of UCB0599 (180mg/day and 360mg/day). In all analyses, the 2 dose levels will be assessed separately against placebo, there will be no pooling of the 2 dose levels, and they will not be compared to each other.

The comparison of the high dose of UCB0599 with placebo will be considered as the primary evaluation. If the comparison of the low dose and placebo gives a positive result on the primary estimand but the comparison of the high dose and placebo does not, these results will have to be interpreted with caution.

PD0053 includes a Screening Period of 3 to 6 weeks (including where available, a wearable sensor familiarization period for those participants who consent to its use), an 18-month Treatment Period (including, where available, a wearable sensor familiarization period for those participants who consent to its use after the Screening Period), and an SFU Period of 1 month. Study participants who complete the Treatment Period will have the option to transition into a dose-blinded extension study, PD0055. In this case, participants will not enter the SFU Period of PD0053.

The study will be conducted utilizing a partly decentralized model, ie, study visits may be composed of a combination of clinic visits and remote visits (except in France; for France-specific requirements, please refer to the protocol). During remote visits, study assessments will be conducted with the study participant from his/her home. This is offered in order to reduce study participant burden and encourage greater study participation. Further details on the decentralized model are given in the study protocol (Section 4.1.1).

However, all assessments necessary for the analyses of the Primary Estimand (i.e. MDS-UPDRS (Part I – III subscales) will be conducted on-site so that the same rater (on-site Clinician) can undertake the MDS-UPDRS assessments for given participant (at the relevant visits). Only safety, PK and exploratory efficacy assessments will be conducted during remote visits, see the schedule of assessments in protocol section 1.3 for details on the exact assessments to be performed.

Participants will be randomized to either UCB0599 360mg/day (180mg BID), UCB0599 180mg/day (90mg BID), or placebo when the IMP for low dose UCB0599 180mg/day (90mg BID) will be available to supply sites so that the final allocation ratio is 1:1:1. Approximately 645 participants will be screened to achieve 450 randomly assigned to study medication and 429 evaluable participants (accounting for study termination prior to month 3), for an estimated total of 143 evaluable participants per treatment group. To balance prognostic factors across treatment groups, randomization of study participants will be stratified using permutation blocks by gender.

The outcomes of this study will inform the design and dose selection for confirmatory studies and help to further validate novel endpoints and technologies and support strategic development program decisions.

The schedule of activities for this study can be found in protocol section 1.3 and the study schematic can be found in protocol section 1.2.

